### **9.2.2 Adverse Event Overview**

The number and percentage of subjects experiencing TEAEs will be summarized by treatment group as specified in Section 6.0 and overall.

An overview of AEs will be presented consisting of the number and percentage of subjects experiencing at least one event for each of the following AE categories:

- All TEAEs
- Treatment-emergent serious adverse events (SAEs)
- Treatment-emergent severe adverse events
- TEAEs reasonably possibly related to study drug
- TEAEs of special interest (AESIs)
- TEAEs leading to discontinuation of study drug

- TEAE leading to death
- All deaths

Additional AEs may be considered for tabulation/summary based on recommendations from Clinical and Safety as deemed appropriate.

For AESIs, the point estimate and 95% CI (using normal approximation) will be provided for the treatment difference in AE percentages.

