5.5 Withdrawal of Subjects and Discontinuation of Study

A subject may voluntarily withdraw or be withdrawn from the study at any time for reasons including, but not limited to, the following:

- Clinically significant abnormal laboratory results or AEs, which rule out continuation of the study drug, as determined by the investigator or the AbbVie Therapeutic Area Medical Director.
- Serious infections (e.g., sepsis) that cannot be adequately controlled within 2 weeks by anti-infective treatment or would put the subject at risk for continued participation in the trial as determined by the Investigator.

- The investigator believes it is in the best interest of the subject.
- The subject requests withdrawal from the study.
- Eligibility criteria violation was noted after the subject started study drug and continuation of the study drug would place the subject at risk.
- Introduction of prohibited medications or dosages and continuation of the study drug would place the subject at risk.
- Subject is non-compliant with tuberculosis (TB) prophylaxis (if applicable) or develops active TB at any time during the study.
- The subject becomes pregnant while on study drug.
- Malignancy, except for localized NMSC or carcinoma in-situ of the cervix.
- Subject is significantly noncompliant with study procedures, which would put the subject at risk for continued participation in the trial.
- Subject develops a gastrointestinal perforation.

In addition, the following discontinuation criteria also apply:

- Subjects not responding to therapy can discontinue study drug (or withdraw from study) at any time for any reason during the study in order to receive standard of care.
- Subjects who demonstrate worsening of joint count (SJC and/or TJC) at 2 consecutive visits (scheduled or unscheduled) should be discontinued from study drug and treated with standard of care at the discretion of the clinician.
- Starting at the Week 18 visit (after the Week 18 assessments have been performed) and at visits thereafter, subjects who fail to achieve at least 20% improvement in TJC and SJC should be discontinued.

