- Starting at the Week 18 visit (after the Week 18 assessments have been performed) and at visits thereafter, subjects who fail to achieve $CDAI \leq 10$ should have background medication(s) adjusted or initiated (i.e., initiation of or change in corticosteroids, NSAIDs, acetaminophen or adding or increasing doses in csDMARDs [restricted to oral or parenteral MTX, sulfasalazine, hydroxychloroquine, chloroquine and leflunomide except the combination of MTX and leflunomide is allowed as per local label]).
- Starting at the Week 18 visit (after Week 18 assessments have been performed) and at visits thereafter, intra-articular, intramuscular, intravenous, trigger point or tender point, intra-bursa, and intra-tendon sheath injections of corticosteroids, dosage and frequency per standard of care are allowed. For the analysis of the TJC and SJC, injected joints will be considered "not assessable" for 3 months from the time of the intra-articular injection.
- Starting at the Week 24 visit and at visits thereafter, subjects achieving 20% improvement in TJC and SJC but not achieving $CDAI \leq 10$ should be considered for discontinuation to standard of care at the discretion of the clinician.

Subjects who prematurely discontinue study drug should complete a Premature Discontinuation (PD) Visit as soon as possible, preferably within 2 weeks of discontinuation. See Section 5.6 for information regarding early discontinuation.

For subjects to be considered lost to follow-up, reasonable attempts must be made to obtain information on the subject's final status. At a minimum, 2 telephone calls must be made and 1 certified letter must be sent and documented in the subject's source documentation.

AbbVie may terminate this study prematurely, either in its entirety or at any site. The investigator may also stop the study at his/her site if he/she has safety concerns. If AbbVie terminates the study for safety reasons, AbbVie will promptly notify the investigator.

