7.3 Statistical Analyses for Efficacy

Analysis of efficacy endpoints will be conducted on the FAS based on treatments as randomized for Study M16-063. The analysis will be based on As Observed data, and no imputation will be conducted. The analysis treatment groups will be described as follows indicating from Study M16-063 to extension Study M16-763:

- Group 1: ABBV-599 to ABBV-599
- Group 2: ABBV-105 60 to 105 60 mg
- Group 3: ABBV-105 20 to 105 20 mg
- Group 4: ABBV-105 5 to 105 5 mg
- Group 5: Upadacitinib 15 to Upadacitinib 15 mg, and
- Group 6: Placebo to ABBV-599
- Group 7: All ABBV-599 (Group 1 and 6)

The baseline for all efficacy analyses in this study will be the baseline in Study M16-063.

There is no primary efficacy endpoint and no formal statistical tests will be applied. Only descriptive statistics will be used for all efficacy endpoints. Descriptive statistics will be provided for each treatment group for all visits. These include the number of observations, mean with 95% confidence interval, standard deviation, median, minimum and maximum for continuous endpoints (or the change from baseline measurements), and frequencies and percentages with 95% confidence interval for binary endpoints.

No missing data imputation will be applied. All efficacy analyses will be based on As Observed analysis, and thus a subject who does not have an evaluation at the primary analysis time point will not be included.

Details on efficacy analyses are provided in the SAP.

Sample Size Estimation

This is the LTE study for Study M16-063. All eligible subjects who completed Study M16-063 will be enrolled in this study if the subject signs and dates the informed consent. Based on discontinuation criteria mandating efficacy, it is estimated that 20 - 60% of subjects (i.e., between 40 and 120 subjects) will ultimately complete the LTE.

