7.4 Statistical Analyses for Safety

All safety analyses will be performed in the Safety Analysis Set.

All treatment-emergent adverse events (TEAEs), SAEs, AEs leading to discontinuation, and AESI will be collected during the study. A TEAE is defined as an event with onset or worsening after the first study dose of study drug and within 30 days after the last dose of study drug administration. The number and percentages of subjects experiencing TEAEs will be tabulated using the Medical Dictionary for Drug Regulatory Activities (MedDRA®) system organ class and preferred term. Summaries (including percentages and event per 100 patient-year) of SAEs, deaths, AEs leading to discontinuation, and AESI will be provided as well. For selected laboratory and vital signs parameters, mean change from baseline and percentage of subject with evaluations meeting pre-defined criteria for Potentially Clinically Important values will be summarized.

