### 2.3 Treatment Assignment and Blinding

Subjects who meet eligibility criteria as specified in Section 5.1 of the protocol and enter the study on ABBV-105, ABBV-599, or upadacitinib from Study M16-063 will continue on their previously-assigned treatment through the end of the LTE study. Subjects who meet eligibility criteria and enter the study on placebo for both ABBV-105 and upadacitinib from Study M16-063 will receive ABBV-599. Study drug treatment assignments include the following:

- Group 1: ABBV-599 (ABBV-105 60 mg and upadacitinib 15 mg) administered once a day (QD),
- Group 2: ABBV-105 60 mg and upadacitinib placebo QD,

- Group 3: ABBV-105 20 mg and upadacitinib placebo QD
- Group 4: ABBV-105 5 mg and upadacitinib placebo QD, and
- Group 5: Upadacitinib 15 mg and ABBV-105 placebo QD.

This study plans to enroll subjects who completed Study M16-063 at approximately 39 sites in Canada and the European Union. The number, allocation, and location of sites may vary depending on operational aspects of the study. Study sites and subjects will remain blinded for the duration of the study.

The duration of the LTE study will be approximately 52 weeks. This includes a 48-week double-blind treatment period with study visits conducted at Weeks 18, 24, 30, 36, 48, and 60 from the baseline visit of Study M16-063. In addition, subjects will also have a telephone follow-up call 30 days after their last visit to determine the status of any ongoing AEs/SAEs or the occurrence of any new AEs/SAEs.

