### **9.2 Adverse Events**

Adverse events (AEs) will be summarized and presented using primary MedDRA System Organ Classes (SOCs) and preferred terms (PTs) according to the version of the MedDRA coding dictionary used for the study at the time of database lock. The actual version of the MedDRA coding dictionary used will be noted in the AE tables and in the clinical study report. Specific adverse events will be counted once for each subject for calculating percentages, unless stated otherwise. In addition, if the same adverse event occurs multiple times within a subject, the highest severity and level of relationship to investigational product will be reported.

TEAEs will be summarized using subject data from Study M16-763 and a combination of data from Studies M16-063 and M16-763 that includes any subject receiving a dose in Study M16-763, respectively. Only the datasets from Studies M16-063 and M16-763 that includes any subject receiving a dose in Study M16-763 will be used for per 100 patient years of exposure analyses (for the Study M16-763 study).

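### The AESI treatment difference in SAP 9.2.2 uses crude percentages, so it is biased against the longer-retained arm if retention differs between arms

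*SAP*

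**What the plan says.** SAP 9.2.2 states that, for AESIs, a point estimate and a normal-approximation 95% CI "will be provided for the treatment difference in AE percentages". The arm pairs are not named. SAP 9.2 defines the percentages: "Specific adverse events will be counted once for each subject for calculating percentages, unless stated otherwise". Time at risk does not enter. Every other adverse event output is a per-arm count, percentage, rate or listing; the ANOVA tests in SAP 9.3 and 9.4 concern laboratory values and vital signs.

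Time on drug depends on response. Under Protocol 5.5, from the Week 18 visit, "subjects who fail to achieve at least 20% improvement in TJC and SJC should be discontinued". From Week 24, those who reach 20% improvement but not CDAI 10 or below "should be considered for discontinuation to standard of care at the discretion of the clinician". SAP 2.3 describes a "48-week double-blind treatment period", and Protocol 7.3 expects that because of these criteria "it is estimated that 20 - 60% of subjects (i.e., between 40 and 120 subjects) will ultimately complete the LTE".

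Under SAP 9.2.1 an event is treatment-emergent only up to 30 days after the last dose. Protocol 5.6 keeps subjects in scheduled visits after they stop drug, but later events fall outside that window.

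Exposure-adjusted summaries are planned. Protocol 7.4: "Summaries (including percentages and event per 100 patient-year) of SAEs, deaths, AEs leading to discontinuation, and AESI will be provided as well". SAP 9.2.4 gives event rates per 100 subject-years for TEAEs without naming AESIs, and SAP 9.2 limits per-100-PY analyses to the combined M16-063/M16-763 data. None of these has a between-arm difference or a CI.

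**The concern.** A percentage of subjects with an event grows with the length of the counting window. Here the window is time on drug plus 30 days, and time on drug is partly set by efficacy rules. If arms differ in response, they will tend to differ in exposure, and the difference in percentages will mix toxicity with retention. The error runs against the arm that keeps its subjects. The choice of interval does not matter: an exact CI around the same crude difference would carry the same bias. Long-term safety is part of the primary objective (Protocol 3.1), and this is the one adverse event result that a reader can take as a comparison between treatments.

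**Working it through.** **The plan's own figure.** 40/0.20 = 200 and 120/0.60 = 200, so both ends of the completion estimate imply the same 200 starters. The range is for the whole study; no retention by arm is given.

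**Inputs from the documents.** 48 weeks of treatment; a 30-day tail (4.29 weeks); efficacy stopping from study Week 18 (LTE Week 6) and at later visits, at study Weeks 24, 30, 36 and 48 (LTE Weeks 12, 18, 24 and 36).

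**Assumptions not in the documents.** The same constant first-event hazard h in both arms; completion fractions p by arm; all non-completers stopping at one LTE week s; about 33 subjects per arm (200/6), or 67 if two groups are pooled.

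**Formula.** With F(w) = 1 − exp(−h·w/52.18) and w in weeks:

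- crude % = p·F(48 + 4.29) + (1 − p)·F(s + 4.29)
- bias = (p₁ − p₂)·[F(52.29) − F(s + 4.29)], which is zero when p₁ = p₂.

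**At h = 20/100 PY, s = 12.** F(52.29) = 18.16% and F(16.29) = 6.05%.

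- 60%: 0.6 × 18.16 + 0.4 × 6.05 = 13.3%. 20%: 0.2 × 18.16 + 0.8 × 6.05 = 8.5%. Bias 0.4 × 12.11 = +4.8 points.
- 50% vs 30%: 12.1% vs 9.7%. Bias 0.2 × 12.11 = +2.4 points.

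**Sensitivity at h = 20/100 PY** (differences and ratios from unrounded values):

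| Completion | Stop (LTE week) | Data | Crude % | Difference | Ratio |
|---|---|---|---|---|---|
| 40% vs 40% | 12 | M16-763 | 10.9 vs 10.9 | 0 | 1.00 |
| 50% vs 30% | 12 | M16-763 | 12.1 vs 9.7 | +2.4 | 1.25 |
| 60% vs 20% | 6 | M16-763 | 12.4 vs 6.7 | +5.7 | 1.85 |
| 60% vs 20% | 12 | M16-763 | 13.3 vs 8.5 | +4.8 | 1.57 |
| 60% vs 20% | 24 | M16-763 | 15.0 vs 11.9 | +3.2 | 1.27 |
| 60% vs 20% | 36 | M16-763 | 16.6 vs 15.1 | +1.5 | 1.10 |
| 60% vs 20% | 12 | combined (12 more weeks for all) | 17.2 vs 12.6 | +4.6 | 1.37 |

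**Less common events.** At h = 5/100 PY, s = 12, 60% vs 20%: 0.4 × (4.89 − 1.55) = +1.3 points (+1.6 if every stop fell at LTE Week 6).

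**Precision of the planned CI.** Half-width = 1.96·√[(a(1 − a) + b(1 − b))/n], where a and b are the two crude proportions. For 60% vs 20% and s = 12 it is about ±15 points (33 per arm) or ±10.5 (67) at 20/100 PY, and ±8.1 or ±5.7 at 5/100 PY.

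**Does a first-event rate remove the bias?** With a constant hazard, expected time to first event or window end is F(w)/h years, so events divided by time returns h whatever the retention. At h = 20/100 PY, s = 12, mean time at risk is 0.666 years (60% completing) and 0.424 years (20%): 0.1332/0.666 = 0.1 × 2.0 and 0.0847/0.424 = 0.1 × 2.0, that is 20 per 100 PY in each arm. A simulation of 20,000 trials with stopping spread evenly over time (60% vs 20%; h = 10, 20 or 50/100 PY; 33 or 67 per arm) agrees. The rate difference averaged within ±0.21 per 100 PY of zero, while the crude difference averaged +2.4 to +9.7 points.

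**The case against.** The strongest reply is that the plan does not ignore exposure. Protocol 7.4 promises AESI rates per 100 PY, SAP 9.2.4 gives TEAE rates, and SAP 6.0 tabulates duration by group, so a reader can see unequal exposure. That stands, and it narrows the point: what is missing is an exposure-adjusted contrast with an interval. The planned rate is also not a clean substitute. Its numerator includes the 30-day tail while its denominator is drug exposure only. At equal hazards of 20/100 PY on combined data (60% vs 20%, stopping spread evenly) it gives about 21.7 vs 22.4.

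Second, Protocol 4.2 makes the primary comparison each arm against its own profile in the feeder study. The AESI difference is one sentence in an overview section, with no decision rule. That also stands and limits the consequences.

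Third, a reader might infer from the 20–60% range that arms will differ as widely as 60% vs 20%. The documents do not support this: the range expresses uncertainty about completion overall, and equal retention is compatible with it.

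Fourth, a reader might infer that the crude difference will hide a real signal. Under the outer assumptions with LTE Week 12 stops, hazards of 20 vs 32/100 PY do give 13.3% vs 13.1%. But the rate difference of 12 per 100 PY would itself have a 95% CI of roughly ±35 (33 per arm) or ±25 (67 per arm). Exposure adjustment centres the estimate correctly; it does not make so small a study conclusive.

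**Conclusion.** The concern holds conditionally. If retention differs between arms, the planned AESI difference is biased against the longer-retained arm at equal hazards, and nothing else in the plan supplies a corrected contrast. The direction is certain under that condition; the size is not. A moderate assumption (50% vs 30%) gives a ratio of about 1.25 at 20/100 PY with LTE Week 12 stops. The outer case (60% vs 20%) gives 1.57, falling to about 1.27 or 1.10 with later stops and about 1.37 on combined data; it would be higher only if stops clustered at LTE Week 6. For AESIs at or below 5/100 PY the bias is minor beside the CI width, so it matters mainly for the commoner AESIs. The documents do not support the stronger claims that exposure is disregarded, that the arms will differ by the full 20–60% range, or that the study's main safety conclusion depends on this estimate. This is a change that should be made, not a flaw that invalidates the safety analysis.

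**What to change.** In SAP 9.2.2, report the AESI contrast as a difference in exposure-adjusted incidence rates with a 95% CI: subjects with a first event divided by patient-years to first event or to the end of the TEAE window. Name the arm pairs. Amend SAP 9.2, which confines per-100-PY analyses to the combined data, so that the M16-763 period can also be used. Keep the crude percentages as descriptive columns.

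The cost is SAP wording and one table program; no new data are needed. The downsides should be stated with the result. The rates assume a roughly constant hazard. They do not remove bias if subjects who stop for non-response have a different event hazard. At an assumed 33 per arm they will be imprecise: about ±30 per 100 PY for equal hazards of 20/100 PY in the 60% vs 20%, LTE Week 12 case.

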### **9.2.3 Treatment-Emergent Adverse Events by SOC and/or PT**

The number and percentage of subjects experiencing adverse events will be tabulated by SOC and MedDRA PT by "as treated" treatment groups and overall. The SOCs will be presented in alphabetical order, and the PTs will be presented in alphabetical order within each SOC.

The following summaries of adverse events will be generated:

- All TEAEs
- Treatment-emergent serious adverse events (SAEs)
- Treatment-emergent severe adverse events
- TEAEs reasonably possibly related to study drug
- TEAEs leading to discontinuation of study drug
- TEAE leading to death
- Frequent AEs (reported in 2% of subjects or more in any treatment group)

Subjects reporting more than one adverse event for a given MedDRA preferred term will be counted only once for that term (most severe incident for the severity tables and most related incident for the relationship tables). Subjects reporting more than one type of adverse event within a SOC will be counted only once for that SOC. Subjects reporting more than one type of adverse event will be counted only once in the overall total. In addition, if the same adverse event occurs multiple times within a subject, the highest

severity and level of relationship to investigational product will be reported. In addition, TEAEs will be summarized by PT and sorted by decreasing frequency for the total active group.

#### **9.2.4 Treatment-Emergent Adverse Events per Patient-Years of Exposure**

TEAEs occurring during Study M16-063 and Study M16-763 will be summarized by event rate per 100 subject years, defined as

$$100 * (\text{Number of TEAEs}) / (\text{Total Patient Years})$$

where total patient years is defined as the sum of the study drug exposure of all subjects normalized by 365.25 and rounded to 1 decimal place.

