An important medical event that may not be immediately life-threatening or result in death or hospitalization, but based on medical judgment may jeopardize the subject and may require medical or surgical intervention to prevent any of the outcomes listed above (i.e., death of subject, life threatening, hospitalization, prolongation of hospitalization, congenital anomaly, or persistent or significant disability/incapacity). Additionally, any elective or spontaneous abortion or stillbirth is considered an important medical event. Examples of such events include allergic bronchospasm requiring intensive treatment in an emergency room or at home, blood dyscrasias or convulsions that do not result in inpatient hospitalization, or the development of drug dependency or drug abuse.

All AEs reported from the time of study drug administration until 30 days after discontinuation of study drug administration will be collected, whether solicited or spontaneously reported by the subject. In addition, SAEs and protocol-related nonserious AEs will be collected from the time the subject signs the study-specific informed consent.

AbbVie will be responsible for Suspected Unexpected Serious Adverse Reactions (SUSAR) reporting for the Investigational Medicinal Product (IMP) in accordance with global and local requirements.

AEs will be monitored throughout the study to identify any of special interest that may indicate a trend or risk to subjects.

Adverse Events of Special Interest

The following adverse events of special interest (AESI) will be monitored during the study:

- Serious infections
- Opportunistic infections
- Herpes zoster
- Tuberculosis
- Malignancy (all types)
- Gastrointestinal perforations
- Adjudicated cardiovascular events (e.g., major adverse cardiovascular event [MACE])
- Anemia
- Neutropenia

- Lymphopenia
- Increased serum creatinine and renal dysfunction
- Hepatic events and increased hepatic transaminases
- Elevated creatine phosphokinase
- Embolic and thrombotic events (non-cardiac, non-CNS)

Adverse Event Severity and Relationship to Study Drug

The investigator will rate the severity of each AE according to the Rheumatology Common Toxicity Criteria v.2.0. **If no grading criteria are provided for the reported event, then the event should be graded as follows:**

- Mild (Grade 1): Asymptomatic or mild symptoms; clinical or diagnostic observations only; intervention not indicated.

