## 6.0 Study Drug Duration and Compliance

A summary of study drug duration (days) will be provided by each treatment arm for the Safety Analysis Set.

The duration of exposure to study drug will be summarized by groups as specified below.

- Group 1: ABBV-599 Always
- Group 2: ABBV-105 60 mg
- Group 3: ABBV-105 20 mg
- Group 4: ABBV-105 5 mg
- Group 5: Upadacitinib
- Group 6: ABBV-599 After Placebo
- Group 7: Placebo (Not present in Study M16-763)

The duration of exposure to study drug will be summarized for each group as specified above, with the number of subjects, mean, standard deviation, median, minimum and maximum values. In addition, the number and percentage of subjects exposed to study drug will be summarized for Study M16-063/763 combined and for Study M16-763 treatment period only respectively. For Study M16-063/763 combined, the following duration intervals will be used:

- $\geq 1$  day
- $\geq 15$  days
- $\geq 29$  days

- $\geq 57$  days
- $\geq 85$  days
- $\geq 127$  days
- $\geq 169$  days
- $\geq 211$  days
- $\geq 252$  days
- $\geq 336$  days
- $\geq 420$  days

The exposure to study drug in days for Study M16-063/763 combined period is calculated as:

Exposure = (date of last study medication in Study M16-763 – date of first study medication in Study M16-063 + 1)

For Study M16-763 only, the following duration intervals will be used:

- $\geq 1$  day
- $\geq 42$  days
- $\geq 85$  days
- $\geq 127$  days
- $\geq 168$  days
- $\geq 252$  days
- $\geq 336$  days

The exposure to study drug in days for Study M16-763 period only is calculated as:

Exposure = (date of last study medication in Study M16-763 – date of first study medication in Study M16-763 + 1)

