### **9.2.1 Treatment-Emergent Adverse Events**

To summarize data from Study M16-763 only, a treatment-emergent Adverse Event (TEAE) is defined as an adverse event with an onset date that is on or after the first dose of study drug from Study M16-763, and no more than 30 days after the last dose of study drug from Study M16-763.

To summarize a combination of data from Studies M16-063 and M16-763, a treatment-emergent Adverse Event (TEAE) is defined as an adverse event with an onset date that is on or after the first dose of study drug from Study M16-063, and no more than 30 days after the last dose of study drug from Study M16-763.

Events where the onset date is the same as Study M16-063 study drug start date are assumed to be treatment-emergent. If an incomplete onset date was collected for an adverse event, the event will be assumed to be treatment-emergent unless there is other evidence that confirms that the event was not treatment-emergent (e.g., the event end date was prior to the study drug start date).

The number and percentage of subjects experiencing TEAEs will be summarized.

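### Adverse-event rates count events to 30 days after last dose but patient-years stop at last dose, so the rates are modestly overstated and depend on length of exposure

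*SAP*

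**What the plan says.** **Numerator.** SAP 9.2.4 states that "TEAEs occurring during Study M16-063 and Study M16-763 will be summarized by event rate per 100 subject years". The count is of events, not of subjects. For the combined data of the two studies, SAP 9.2.1 accepts as treatment-emergent any event with onset from the first dose in M16-063 "and no more than 30 days after the last dose of study drug from Study M16-763". Protocol 7.4 sets the same limit, "within 30 days after the last dose of study drug administration". Protocol 6.1 supports it on the collection side: adverse events "until 30 days after discontinuation of study drug administration will be collected".

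**Denominator.** In SAP 9.2.4 the denominator is total patient-years, "where total patient years is defined as the sum of the study drug exposure of all subjects normalized by 365.25". SAP 6.0 defines exposure for the combined period as "Exposure = (date of last study medication in Study M16-763 – date of first study medication in Study M16-063 + 1", with nothing added after the last dose.

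**Data set.** SAP 9.2 bases the rates on combined M16-063 and M16-763 data, restricted to subjects dosed in M16-763.

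Neither document limits the numerator of the rate to events on drug, and neither adds the 30 days to the patient-years.

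**The concern.** A rate per patient-year needs events and time taken from the same window. Here each subject can contribute events for up to 30 days during which no time is counted. The convention does little harm when exposure is long and few subjects stop early. In this study SAP 2.4 expects only 20% to 60% to complete, and Protocol 5.5 calls for efficacy-driven discontinuation from Week 18. Many subjects may therefore have short exposure, for which 30 days is a larger share.

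The rates matter because long-term safety is part of the primary objective. Protocol 7.4 asks for events per 100 patient-years for SAEs, deaths, adverse events leading to discontinuation and events of special interest. When follow-up is unequal, these are the summaries that adjust for exposure; simple percentages do not.

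**Working it through.** The documents state no adverse-event rate or patient-year total, so there is no planned figure to reproduce. The check works from the definitions.

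**Inputs from the documents**
- Week 60 from M16-063 baseline (SAP 2.3): 60 × 7 = 420 days for a completer.
- Completion of 20% to 60% (SAP 2.4).
- Tail of 30 days (SAP 9.2.1).

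**Assumptions**
- All non-completers stop at Week 18 (126 days) or all at Week 36 (252 days).
- The full 30-day tail is observed for everyone.
- Exposure runs from the first M16-063 dose, as the SAP 6.0 formula reads. How placebo time is handled for subjects moving to ABBV-599 is a separate question and is not used here.

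**Formula.** Let T be mean exposure in days. The SAP rate is events over (T + 30) days divided by T. A matched rate divides the same events by T + 30. The ratio of the two is (T + 30)/T, an excess of 30/T. The numerator is the same in both, so this ratio does not depend on the event rate in the tail.

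**One completer.** 30/420 = 7.1%.

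**At the stated completion range.** With completion c and stop day s, T = 420c + (1 − c)s.

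| Completion | Stop day | T (days) | Excess 30/T |
|---|---|---|---|
| 60% | 252 | 252 + 100.8 = 352.8 | 8.5% |
| 60% | 126 | 252 + 50.4 = 302.4 | 9.9% |
| 20% | 252 | 84 + 201.6 = 285.6 | 10.5% |
| 20% | 126 | 84 + 100.8 = 184.8 | 16.2% |

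**Extreme split between arms.** Suppose one arm had 20% completion, another had 60%, and their true rates were equal. The false rate ratio would be:
- all stop at Week 18: 1.162/1.099 = 1.06;
- all stop at Week 36: 1.105/1.085 = 1.02;
- stops spread evenly over Weeks 18, 24, 30, 36 and 48 (mean 31.2 weeks, 218.4 days): T = 258.7 and 339.4 days, factors 1.116 and 1.088, ratio 1.03.

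**Illustration in event counts.** Assume 40 subjects per arm, a true rate of 200 events per 100 patient-years that continues through the tail, and all stops at Week 18. Rates below use unrounded event counts and patient-years rounded to one decimal, as the SAP specifies.
- 20% completion: 47.0 expected events. Over 20.2 patient-years the SAP rate is 232.9; over the matched 23.5 it is 200.2.
- 60% completion: 72.8 expected events. Over 33.1 patient-years the SAP rate is 220.0; over the matched 36.4 it is 200.0.

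**If the target is instead the rate on drug.** Let r be the tail event rate divided by the on-drug rate. The SAP rate then exceeds the on-drug rate by r × 30/T. With r = 0.5 (assumed) and stops at Week 18, the excess is 8.1% at 20% completion and 5.0% at 60%.

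**The case against.** **The contrast between arms is hypothetical.** A reader might infer that the plan will make better-retained arms look safer by 2% to 6%. The documents do not support that as a forecast. The 20% to 60% in SAP 2.4 is an uncertainty range for the whole study, and no completion figure is given by arm. Placing one arm at each end is the extreme split of that range, and the upper figure also needs every non-completer to stop at Week 18. The base of 200 (40/0.20 = 120/0.60) is not defined either. If it includes subjects who never enter the extension, completion among dosed subjects is higher and the effect smaller. This objection stands.

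**The tail may be incomplete.** Under Protocol 5.6 the 30-day call is optional for subjects who withdraw consent. At the interim, subjects still on drug have no tail yet. Both reduce the excess. This also stands, although Protocol 5.6 asks subjects who only stop drug to keep attending visits.

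**No planned inference rests on these rates.** Protocol 4.2 makes the primary comparison each arm against its own M16-063 profile. SAP 9.2.2 compares percentages, not rates, for events of special interest, and SAP 9.2.4 plans no test or interval. In the illustration, Poisson error alone gives a 95% factor of exp(1.96 × √(1/47.0 + 1/72.8)) = 1.44 either way on the rate ratio, far more than 1.06. This bears on importance; it does not remove the mismatch.

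**Extending the denominator is not the only valid repair.** With r = 0.5 and stops at Week 18, the extended-denominator rate relative to the on-drug rate is (184.8 + 15)/214.8 = 0.930 at 20% completion and (302.4 + 15)/332.4 = 0.955 at 60%, a ratio of 0.974. The SAP rate gives 1.081/1.050 = 1.03. If an on-drug rate is wanted, extending the denominator errs by a similar amount the other way. The choice therefore depends on which rate the sponsor intends, and the SAP does not say.

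**Conclusion.** The mismatch is explicit in SAP 6.0, 9.2.1 and 9.2.4, and nothing in either document resolves it. Its direction against a matched denominator is upward. Its size is modest: about 7% for a completer and about 8.5% to 16% at 60% to 20% completion, given a fully observed tail and the assumed stopping times.

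The effect on comparisons between arms is conditional. If retention differs, the arm with shorter exposure carries the larger excess. Whether retention will differ, and in which arms, cannot be read from the documents. The 2% to 6% is an extreme-case figure, well inside the noise of descriptive rates. Subject percentages do not use this denominator and are unaffected. This is a small point of definition, worth correcting because the correction is cheap and these rates report a primary safety objective.

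**What to change.** State in SAP 9.2.4 which rate is intended, and use one window for both parts:
- **Rate over the treatment-emergent window:** define patient-years for the rate as first dose to the earlier of last dose + 30 days and last contact.
- **Rate on drug:** keep patient-years as they are and restrict the numerator of the rate to events with onset up to the last dose. Events in the tail would still appear in the percentage tables.

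Keep drug-exposure days in SAP 6.0 for the exposure table. If consistency across the programme is needed, keep the current rate and show the matched rate beside it.

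The cost is one sentence in the SAP and one derived variable. The downside is that the rates will differ slightly from other programme tables.
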